9.10. Other aspects

VIR-Life is the roll-over non-interventional study following GEMINIS. The study is designed to enable the prospective evaluation of the real-life treatment outcomes of Viread for a total of 6 years. This implies that the sample size is predefined by the number of available patients rolling over from GEMINIS.

10. PROTECTION OF HUMAN SUBJECTS

10.1. Good Pharmacoepidemiology Practices

The investigator will conduct this study in accordance with the laws and regulations of the country and the guidelines of Good Pharmacoepidemiology Practices (GPPs), Heads of Medicines Agencies (HMA) Good Pharmacovigilance Practices (GVP) including archiving of essential documents.

10.2. Institutional Ethics Committee (IEC) Review

The protocol and any accompanying material to be provided to the subject (e.g. subject information sheets, or descriptions of the study used to obtain informed consent) will be submitted to an *IEC*. The investigator will not begin to document data until approval from the *IEC* has been received.

10.3. Informed Consent

The investigator is responsible for obtaining written informed consent from each individual participating in this study after adequate explanation of the aims, methods and objectives of the study. The investigator must utilize the most current IEC approved consent form for documenting written informed consent. Each informed consent will be appropriately signed and dated by the subject and the person conducting the consent discussion.

10.4. Confidentiality

Subjects' anonymity will be strictly maintained. Only a unique subject identification code and the year of birth will be recorded in the eCRF system

The investigator agrees that all information received from Gilead remain the sole and exclusive property of Gilead during the conduct of the study and thereafter. This information is not to be disclosed to any third party (except employees or agents directly involved in the conduct of the study or as required by law) without prior written consent from Gilead. The investigator further agrees to take all reasonable precautions to prevent the disclosure by any employee or agent of the study site to any third party or otherwise into the public domain.

11. MANAGEMENT AND REPORTING OF ADVERSE EVENTS

11.1. Adverse Events

An **adverse event** (AE) is any untoward medical occurrence in a clinical study subject administered a pharmaceutical product, which does not necessarily have a causal relationship with the treatment. An AE can therefore be any unfavorable and/or unintended sign, symptom, or disease temporarily associated with the use of a medicinal product, whether or not considered related to the medicinal product. AEs may also include lack of efficacy, overdose, medication error, drug abuse/misuse reports or reports of AEs in infants following exposure from breastfeeding. Preexisting events that increase in severity or change in nature during this non-interventional study will also be considered AEs.

An AE does not include the following:

- Medical or surgical procedures such as surgery, endoscopy, tooth extraction, and transfusion. The condition that led to the procedure may be an AE and should be reported.
- Situations where an untoward medical occurrence has not occurred (eg, hospitalization for elective surgery, social and/or convenience admissions)
- Any medical condition or clinically significant laboratory abnormality with an onset date before the consent form is signed. These are considered to be preexisting conditions and should be documented on the medical history CRF (if applicable).

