	 Weight Serum HBV-DNA concentration HBeAg, anti-HBe; HBsAg, antiHBs ALT-level Serum creatinine, eCrCL, serum phosphorus Albumine, Bilirubine, Thrombocytes, Prothrombine time (i.e. Quick value) Liver histology staging, transient elastography HCC development Co-morbidities, Incident co-infections with HIV, HCV or HDV Amount of alcohol consumption Adverse events Special Situations; pregnancies, medication error, abuse, misuse, overdose, lack of effect, adverse events in infants following exposure from breastfeeding and adverse events associated with product complaints Dosing of Viread[®] Reason for discontinuation of Viread[®], if applicable 		
Data Sources:	Collection of routine visit data via eCRF		
Study Size:	250 patients		
Data Analysis:	 Descriptive analysis: Categorical and ordinal variables will be described by sample size and the frequency of each modality (over the total number of responses). Quantitative variables will be described by the number of responses, mean, standard deviation, minimum, maximum & madian of all available data. 		

	• Inferential analysis:
	When deemed necessary, sub-group comparisons and/or between time point comparisons may be implemented.
	• Multivariate analysis:
	The potential dependence of treatment outcome frequency with other outcome variables or baseline characteristics will be investigated through methods of multivariate analysis.
Milestones:	Start of data collection : approx. May 2013
	End of Data collection: December 2016
	Interim analysis: planned for Sept. 2014 (year 4 data) and Sept. 2015 (year 5 data)
	Final Study report: April 2017 (year 6 data)
	Publication: submission in Q2-3 2017

This study will be conducted in accordance with the guidelines of Good Pharmacoepidemiology Practices (GPPs), Heads of Medicines Agencies (HMA) and Good Pharmacovigilance Practices (GVP) including archiving of essential documents.

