7.3. GEMINIS

The GEMINIS Study

GEMINIS was the first prospective non-interventional observational study on the real-life treatment outcomes and the patterns of use of three years of Viread[®] in Germany. The study recruited adult patients with HBV mono-infection. At inclusion, patients were TDF-naïve, however, previous treatment for CHB was accepted. Documentation and treatment decisions were at the sole discretion of the participating physician.

Baseline Characteristics

35 centers (20% hospitals, 80% office-based) enrolled 400 CHB patients from May 2009 - May 2010. Most frequent countries of birth were: 31% Germany, 19% Turkey, 8.5% Russia, 6.5% Vietnam, 3% Poland. The main reason for using Viread[®] was persistent viremia (25%) or virologic relapse despite previous treatment (10%). 90% initiated TDF monotherapy. Additional baseline characteristic are summarized in table 1.

Age • mean (+/-SD) [years]	44.5 (+/- 13.8)
• 18-65; > 65 [years]	91%; 9%
Male	69%
Caucasian	76%
ALT > ULN*	55%
HBeAg-negative	69%
Serum HBV DNA[IU/ml]Median (IQR)• entire group $(N=400)$ • naïve patients $(n=183)$ • experienced patients $(n=217)$	40-4.0x10 ⁵) 8x10 ³ - 6.8x10 ⁶) 20 - 2.0x10 ⁴)
Treatment naïve	46%
Biopsy done (fibrosis score $\geq 2^{**}$)	14% (37%)
Elastography data (advanced fibrosis***)	17% (22%)
Cirrhosis***	11%
TDF monotherapy	92%
*ULN: Male \leq 43 IU/L, female \leq 34 IU/L; by physician	**by Desmet-Scheuer or Metavir; *** as defined

Table 1: Baseline patient characteristics

GEMINIS – Results after 24 month of follow up

Viread[®] was primarily used as monotherapy. After 24 month of follow up, HBV replication was suppressed through 24 months in the majority of treatment naïve and experienced patients, regardless of pre-treatment status. HBeAg-loss/-seroconversion was documented in 23 % and 19 % of HBeAg+ patients, respectively. A 5.1 % cumulative probability for HBsAg-loss in HBeAg+ patients was observed. This rate is comparable to the 96 week result of TDF registration study 103 [24]. Two patients HBeAg-negative at baseline lost HBsAg. The overall safety profile of Viread[®], including renal safety, was very favorable in this real-life setting (Table 2) [28].

	Treatment- naïve (n=183)	Treatment - experienced (n=217)		
HBV-DNA < 169 IU/ml • HBeAg-positive • HBeAg-negative • prior LAM+ADV • prior ETV	88 % 94 % NA NA	94 % 97 % 100 % 96 %		
HBV-DNA < 69 IU/ml • HBeAg-positive • HBeAg-negative • prior LAM+ADV • prior ETV	81 % 80 % NA NA	84 % 90 % 89 % 92 %		

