9.2.3. Prevention of bias

- In GEMINIS all centers with large (>100) CHB patient volume were invited to participate in the study, however, disproportionate distributions across the federal states of Germany were expected due to the unequal distribution of prevalence of chronic hepatitis B.
- GEMINIS was open for all patients chronically (mono-) infected with Hepatitis B Virus, potentially eligible for treatment under current guidelines as stated earlier in the introduction section. Enrollment was allowed for to up to 400 patients treated with Viread[®].
- To combat selection bias the participating sites in GEMINIS were asked to enroll every single new patient qualifying for inclusion until the NIS is fully recruited.
- For VIR-Life, all eligible GEMINIS patients remaining in the 25 participating sites are asked to be rolled over into the VIR-Life study
- For all eligible patients not enrolling into VIR-Life the sites have to document respective reasons (lost to follow-up, no signed ICF, death).

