9.4.1. Baseline

VIR-life is the extended follow up of GEMINIS. Therefore, VIR-life baseline data is the data that was collected at GEMINS baseline.

9.4.2. During VIR-Life follow up and at end of follow up (month 48, 60 and 72):

- HBV- virology and serology parameters
- Biochemical serum-parameters
 - ALT
- Renal safety parameters
 - Serum creatinine, eCrCl, serum phosphorus
- Liver synthesis parameters
 - Albumin, bilirubin, thrombocytes, prothrombin time (Quick-Value)
- Liver histology, elastography, incident HCC
- Co-morbidities, Co-infections, alcohol consumption
- Adverse events
- Special Situations; pregnancies, medication error, abuse, misuse, overdose, lack of effect, adverse events in infants following breastfeeding, and adverse events associated with product complaints
- Dosing of Viread[®]
- Combination therapy
- Reason for discontinuation of Viread[®], if applicable

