11.2.1. Assessment of Causality for Study Drugs and Procedures

The investigator or qualified subinvestigator is responsible for assessing the relationship to drug therapy using clinical judgment and the following considerations:

- No: Evidence exists that the AE has an etiology other than the drug. For SAEs, an alternative causality must be provided (eg, preexisting condition, underlying disease, intercurrent illness, concomitant medication).
- Yes: A temporal relationship exists between the AE onset and administration of the drug that cannot be readily explained by the subject's clinical state or concomitant therapies. Or, the AE appears with some degree of certainty to be related, based on the known therapeutic and pharmacologic actions or AE profile of the drug. In case of cessation or reduction of the dose, the AE may abate or resolve and it may reappear upon rechallenge.

It should be emphasized that ineffective treatment should not be considered as causally related in the context of AE reporting.

11.3. Investigator Requirements and Instructions for Reporting Adverse Events and Serious Adverse Events to the CRO

During the defined study period (month 36 to months 72), each investigator has to document all Adverse Events he becomes aware of including seriousness and causality in the eCRF system within 24 hours. These are automatically forwarded via the eCRF system to the CRO safety department.

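### Section 11.3 asks for all adverse events from month 36, but Section 11.1 rules out anything with onset before consent, and for most patients consent probably comes after month 36

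*Protocol*

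**What the plan says.** The protocol has two rules on which events count.

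- Section 11.3 sets the reporting period: "During the defined study period (month 36 to months 72), each investigator has to document all Adverse Events he becomes aware of".
- Section 11.1 lists what an adverse event does not include. The third item is "Any medical condition or clinically significant laboratory abnormality with an onset date before the consent form is signed". Such conditions are treated as pre-existing and go to the medical history form, if applicable. The same section makes one exception: "Preexisting events that increase in severity or change in nature during this non-interventional study will also be considered AEs".

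Other sections fix the calendar and the denominator.

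- Month 0 is the GEMINIS baseline (Section 9.4.1): "VIR-life baseline data is the data that was collected at GEMINS baseline".
- GEMINIS "enrolled 400 CHB patients from May 2009 - May 2010" (Section 7.3).
- The synopsis milestones give "Start of data collection : approx. May 2013", and Section 6 repeats the date.
- Section 10.3 requires written consent for this study, but gives no date and no link to month 36.
- Section 9.2 admits patients who have completed three years in GEMINIS and are still on a Viread-containing regimen.
- Section 9.7 counts person-time from baseline to discontinuation in any time-to-event analysis.
- Section 9.2.3 has sites record why an eligible patient did not enrol: "lost to follow-up, no signed ICF, death".

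**The concern.** The reporting period opens at a fixed study month, while the definition of an adverse event opens at a signature. The two agree only if consent is signed by month 36, and nothing in the protocol requires that. Take a patient with a new event at month 40 who signs at month 46: Section 11.3 says to document the event and Section 11.1 says it is not an adverse event. Sites may resolve this differently, and the analysis cannot correct for that afterwards.

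This is a post-authorization safety study with a secondary objective of describing safety and tolerability over six years, including adverse drug reactions. If Section 11.1 is followed, new-onset events in the interval receive no seriousness or causality assessment and do not enter the adverse event or adverse reaction listings. Section 9.7 meanwhile counts the same months as time at risk in any time-to-event analysis. The limitations in Section 9.9 do not mention this.

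**Working it through.** The protocol gives no figure for the interval between month 36 and consent, so the calendar is checked first.

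**Calendar check.** Month k is the enrolment date plus k months.

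| | First GEMINIS patient (May 2009) | Last GEMINIS patient (May 2010) | Last patient plus the 3-month visit window |
|---|---|---|---|
| Month 36 | May 2012 | May 2013 | – |
| Month 48 | May 2013 | May 2014 | Aug 2014 |
| Month 60 | May 2014 | May 2015 | Aug 2015 |
| Month 72 | May 2015 | May 2016 | Aug 2016 |

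The last column falls just before the year 4 interim (September 2014), the year 5 interim (September 2015) and the end of data collection (December 2016). The mapping therefore agrees with the protocol's own milestones. When data collection starts, the earliest patients are already at month 48.

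**Interval between month 36 and consent.** Interval = max(0, consent date − (enrolment date + 36 months)).

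Assumptions: one common consent date, GEMINIS enrolment uniform over its 12 months, 250 patients, no dropout. The planned period is 250 × 3 years = 750 patient-years.

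Consent in May 2013:
- First patient: May 2013 − May 2012 = 12 months, which is 12/36 = 33% of the reporting period. Last patient: 0.
- Mean: (12 + 0)/2 = 6 months.
- Patient-years: 250 × 6/12 = 125, and 125/750 = 16.7%.

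Consent in February 2013. This is tested because the reference list shows web pages accessed on 18 February 2013, and the protocol and consent form still had to go to the ethics committee:
- Maximum: 9 months. Only those enrolled in the first 9 of the 12 months have an interval, 9/12 = 75% of patients.
- Mean: 9²/(2 × 12) = 3.375, about 3.4 months.
- Patient-years: 250 × 3.375/12 = 70.3, and 70.3/750 = 9.4%.

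| Common consent date (assumption) | Range, months | Mean, months | Patient-years of 750 | Share |
|---|---|---|---|---|
| Feb 2013 | 0–9 | 3.4 | 70.3 | 9.4% |
| May 2013 | 0–12 | 6.0 | 125.0 | 16.7% |
| Aug 2013 | 3–15 | 9.0 | 187.5 | 25.0% |
| Nov 2013 | 6–18 | 12.0 | 250.0 | 33.3% |

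Twelve months is thus the maximum at a May 2013 start. It is neither the typical value nor a ceiling.

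**The case against.** The strongest reply is that the two sections can be read together: 11.3 sets the outer period, and 11.1 defines what counts within it. That reading removes the clash of wording but not the consequence, because new-onset events before consent then drop out and the protocol does not say so.

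Several other objections stand and limit the point.

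- A reader might infer that all safety information from the interval is lost. It is not. Conditions may reach the medical history form, later worsening counts as an adverse event, and Sections 9.3 and 9.4.2 collect renal laboratory values, incident HCC, co-infections, co-morbidities and dosing independently of the adverse event definition. What drops out is the adverse event and adverse reaction record. An event that resolved before consent has no later worsening to report.
- A reader might infer that nobody could consent before May 2013. The protocol does not say this. That date is the approximate start of data collection, and Section 10.2 bars documentation, not consent, before ethics approval.
- A reader might take 17% as the error in a planned adverse event rate. No such rate is specified. Section 9.7 applies person-time to any time-to-event analysis and otherwise describes categorical variables by frequencies.
- The protocol does not claim complete capture. Section 11.3 is limited to events the investigator becomes aware of, and Section 9.9 warns of missing data.
- Whether GEMINIS recorded events after its month 36 is not stated. If it did, part of the interval is covered.
- Section 9.2 does not say whether still receiving Viread is judged at month 36 or at consent, so it cannot be asserted that patients who stopped in between are ineligible.

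**Conclusion.** The conflict between Sections 11.1 and 11.3 is real, and nothing else in the protocol resolves it. It is a rule fixed badly, not detail left for a later analysis plan, because it governs what sites record.

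If consent begins around May 2013, the affected interval is 0 to 12 months per patient, mean about 6, or about 125 of 750 planned patient-years (17%). With consent from February 2013 it is up to 9 months, mean about 3.4 (9%); later consent makes it longer. These figures rest on an assumed common consent date, uniform GEMINIS enrolment and no dropout. They measure the time exposed to the conflict, not a number of missed events, which the protocol does not allow one to estimate.

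If Section 11.1 is applied, any time-to-event analysis of adverse events would count this interval as time at risk without recording its new-onset events, which pushes the apparent frequency down. The primary HBV-DNA objective is not affected, and neither are the renal laboratory values collected at visits.

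**What to change.** Reconcile the two sections in one of two ways.

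- **(a) Record the interval.** Amend the third exclusion in Section 11.1 so that events with onset after GEMINIS month 36 are taken from the medical record as adverse events, where consent allows, with a flag for onset before VIR-Life consent. Show them separately, because they are retrospective and come only from patients who went on to enrol.
- **(b) Start at consent.** Change Section 11.3 so that adverse event ascertainment begins at consent, start adverse event person-time on that date as well, and state in Section 9.9 and in the report that coverage between month 36 and consent is incomplete.

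Under either option, tabulate the deaths that Section 9.2.3 already has sites document as reasons for non-enrolment next to the safety results. Do not collect further data on people who did not consent. If GEMINIS did record events after month 36, say so and describe how they will be used.

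The cost is modest. Option (a) needs wording changes, one eCRF flag, a check of the consent text and a look back through charts that sites already transcribe from. Option (b) needs wording and a consent date for each patient in the analysis data, but gives up the interval.

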11.1.1. Adverse Reactions

An **adverse reaction** (AR) is defined as an untoward medical occurrence (unintended or noxious responses) considered causally related to an investigational or approved medicinal product at any dose administered. Adverse reactions may arise from medication errors, uses outside the prescribing information (off-label use), misuse and abuse of the product, overdose, or occupational exposure.

11.1.2. Serious Adverse Events

A serious adverse event (SAE) is defined as an event that, at any dose, results in the following:

- Death
- Life-threatening (Note: The term "life-threatening" in the definition of "serious" refers to an event in which the subject was at risk of death at the time of the event; it does not refer to an event that hypothetically might have caused death if it were more severe.)
- In-patient hospitalization or prolongation of existing hospitalization
- Persistent or significant disability/incapacity
- A congenital anomaly/birth defect
- A medically important event or reaction: such events may not be immediately lifethreatening or result in death or hospitalization but may jeopardize the subject or may require intervention to prevent one of the other outcomes constituting SAEs. Medical and scientific judgment must be exercised to determine whether such an event is a reportable under expedited reporting rules. Examples of medically important events include intensive treatment in an emergency room or at home for allergic bronchospasm; blood dyscrasias or convulsions that do not result in hospitalization; and development of drug dependency or drug abuse. For the avoidance of doubt, infections resulting from contaminated medicinal product will be considered a medically important event and subject to expedited reporting requirements.

Clarification of Serious Adverse Events

- Death is an outcome of an AE, and not an AE in itself. Therefore, if death occurred, the event that led to death needs to be reported as an SAE.
- Complications that occur during hospitalizations are AEs. If a complication prolongs the hospitalization, is life-threatening, or meets any of the other definitions of an SAE, then it is an SAE.
- "In-patient hospitalization" means the subject has been formally admitted to a hospital for medical reasons, for any length of time. This may or may not be overnight. It does not include presentation and care within an emergency department.

• The investigator should attempt to establish a diagnosis of the event on the basis of signs, symptoms, and/or other clinical information. In such cases, the diagnosis (and not the individual signs/symptoms) should be documented as the AE and/or SAE.

11.1.3. Clinical Laboratory Abnormalities and Other Abnormal Assessments as Adverse Events or Serious Adverse Events

Laboratory abnormalities without clinical significance are not recorded as AEs or SAEs. However, laboratory abnormalities (eg, clinical chemistry, hematology, and urinalysis) that require medical or surgical intervention or lead to drug interruption, modification, or discontinuation must be recorded as an AE, as well as an SAE, if applicable. In addition, laboratory or other abnormal assessments (eg, electrocardiogram, x-rays, vital signs) that are associated with signs and/or symptoms must be recorded as an AE or SAE if they meet the definition of an AE or SAE as described in Section 10.1. If the laboratory abnormality is part of a syndrome, record the syndrome or diagnosis (eg, anemia), not the laboratory result (ie, decreased hemoglobin).

11.2. Assessment of Adverse Events and Serious Adverse Events

The investigator or qualified subinvestigator is responsible for assessing AEs and SAEs for causality, and for final review and confirmation of accuracy of event information and assessments.

